9. STUDY PROCEDURES

Specific activities for each study visit are listed below.

9.1 Visit 1 (-30 to Day 1): Screening/Baseline

Informed consent may be collected from study subjects up to 30 days before Visit 1. If applicable, qualified subjects can washout from prohibited medications or treatments (see [Section 8.1](#)) prior to their Screening/Baseline Visit once informed consent has been obtained. If washout period exceeds 30 days, re-consent is required. The Screening and Baseline Visit may be completed on the same day, if no washout is required.

At this visit, the investigator or designee will:

- Obtain a signed, written informed consent, and update the Subject Screening and Enrollment Log.
- Confirm the subject meets the inclusion/exclusion criteria.
- Document the information required on the Medical History form.
- Document the information required on the Demographics form.
- Record the subject's prior and/or concomitant medications and therapies/procedures.

If the subject requires washout from previous medications, the remaining activities will be performed after washout is completed and must be completed within 30 days of first visit, or the subject needs to be re-consented.

- Perform a dermatologic exam. Consistent with Exclusion Criterion #18, any subject with a suspicious lesion within the treatment area should not be enrolled prior to confirmation that the lesion is not skin cancer. In the event that a biopsy is warranted to make such a determination per the investigator, such a procedure is considered outside the scope of this study and therefore will be the responsibility of the potential subject. In the event that a biopsy is needed and it is not available for review, the subject shall be considered a screen failure.
- Identify the 25 cm² treatment area on either the face (excluding ears) or bald scalp. NOTE: Use the procedure as detailed in the Treatment Area Identification Manual to create and label the transparency to record the designated treatment area.
- Create a "subject specific" template per the instructions provided in the Treatment Area Identification Manual to assist the subject in the identification of the treatment area prior to application of the test article. A copy of the template will also be retained in the subject's site file for use by the site to properly identify the treatment area at future visits.
- Take Baseline photographs of the designated 25 cm² treatment area per the instructions provided in the Treatment Area Identification Manual and store one photo in the subject's file at the site and give one photo to the subject in order to help ensure proper application of the test article by the subject.
- Record the size of the designated treatment area.

- Perform the AK lesion count as described in [Section 10.1](#), which includes any AKs ≥ 4 mm in diameter, as well as any smaller lesions. NOTE: A minimum of five to a maximum of 10 AKs >4 mm in diameter in the 25 cm² treatment area is required to qualify.
- Document the diameter of each AK lesion in the treatment area.
- Perform the LSR assessment as described in [Section 10.2](#).
- Reaffirm the Inclusion/Exclusion criteria.
- Perform a UPT for all WOCBP. The UPT must be negative for subjects to continue.
- Assign the subject the next available (lowest) subject number in ascending order. Assign the subject the lowest available test article kit number and dispense test article. NOTE: Test article will be weighed prior to being dispensed and the subject will be instructed not to open study supplies at the site.
- Review and dispense a Subject Instruction Sheet to the subject (see [Appendix 1](#)). Instruct the subject to apply test article twice daily, once in the morning and once in the evening, and demonstrate proper test article application using vehicle gel provided for subject training.
- Explain and issue the subject diary.
- Confirm the next appointment.

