5. STUDY POPULATION

5.1 Subject Eligibility

To be included in the study, subjects must meet the following inclusion and none of the exclusion criteria.

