5.1.1 Inclusion Criteria

1. Is an immunocompetent male and/or non-pregnant female, 18 years of age or older.

2. Has provided written informed consent including consent to photography of the treatment area at Visit 1.
3. Is willing and able to apply the test article(s) as directed, comply with study instructions, and commit to all follow-up visits for the duration of the study.
4. Has a clinical diagnosis of actinic keratoses with at least five (5) and no more than ten (10) clinically typical, visible, or palpable, discrete, nonhyperkeratotic, nonhypertrophic, AK lesions, each at least 4 mm in diameter, contained within a continuous 25 cm² treatment area located on the face (excluding ears) or bald scalp¹³.
5. Is in good general health and free of any disease state or physical condition that might impair evaluation of AK lesions or which, in the investigator's opinion, exposes the subject to an unacceptable risk by study participation.
6. If female, must be post-menopausal¹⁴, surgically sterile¹⁵, or use an effective method of birth control^{16,17} with a negative urine pregnancy test (UPT)¹⁸ at the Baseline Visit.

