5.1.2 Exclusion Criteria

1. Is pregnant, breastfeeding, or is planning to become pregnant or breastfeed during the study.
2. Is currently enrolled in an investigational drug or device study.
3. Has used an investigational drug or investigational device within 30 days prior to the Baseline Visit.
4. Subject has hyperkeratotic, hypertrophic (i.e., Grade 3 AKs), or large AKs of any Grade (e.g., AK >1 cm² in size) within the treatment area.
5. Has >10 AKs of any size within the treatment area.

¹³ Bald scalp for the purposes of this study is a scalp where the subject has lost the majority of their hair (well over 50%) within the intended 25 cm² treatment area where the scalp is: a) readily visible and 2) the number of the AKs in the treatment area can be easily seen and counted by the evaluator. It is also important that both the site and subject can repeatedly identify the treatment area to assure accurate repeat therapy by the subject and evaluation by the investigator.

¹⁴ Defined as amenorrhea greater than 12 consecutive months in women 50 years of age and older.

¹⁵ Hysterectomy, bilateral tubal ligation (at least six months prior to initiation of treatment), or bilateral oophorectomy.

¹⁶ Effective forms of birth control include a) hormonal contraceptives [oral, injectable, transdermal or intravaginal] for one full cycle (e.g., four to eight weeks), or intrauterine device (IUD) for one week, for injectable (e.g., Depo-Provera) the requirement is at least seven days after injection, prior to test article application, or b) condom and spermicidal, or diaphragm/cervical cap and spermicidal which are effective as soon as the birth control method is administered properly. Other acceptable forms of birth control include: a) abstinence for subjects who are not sexually active or b) if the subject is in a monogamous relationship with a partner who is sterile (e.g., a vasectomy performed at least six months prior to the subject's initiation of treatment). Subjects who become sexually active or begin to have relations with a partner who is not sterile during the study must agree to use an effective form of birth control for the duration of the study.

¹⁷ Women of childbearing potential (WOCBP) taking hormonal therapy must be on treatment prior to study entry, continued per label, and must not change their dosing regimen during the study.

¹⁸ UPTs must have a minimum sensitivity of 25 mIU β -hCG/mL.

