10.1 Actinic Keratoses Lesion Counts

AK lesions will be counted at Baseline, Day 60/EOT, and Day 90/EOS. At the Baseline Visit (Visit 1), all AK lesions in the 25 cm² treatment area, independent of size, will be identified, counted, and recorded on the transparency. The number and location of AK lesions to be treated that are ≥ 4 mm in diameter and the diameter of each AK lesion in the 25 cm² treatment area will also be documented at the Baseline Visit. The suggested procedure for AK counting and definition of face (excluding ears) and bald scalp will be detailed in a separate document. At the Baseline Visit, the 25 cm² treatment area must include at least five and no more than 10 clinically typical, visible, or palpable, discrete, nonhyperkeratotic, nonhypertrophic, AK lesions, each at least 4 mm in diameter, contained within a continuous 25 cm² treatment area located on the face (excluding ears) or bald scalp. At the EOT and EOS visits, the number of total AK lesions in the 25 cm² treatment area will be counted and the number of new AKs will be identified. A new AK is defined as a lesion that was not present at the Baseline Visit.

NOTE: To ensure accurate identification of the treatment area, the site must use the transparency and the Baseline photo as necessary to locate the selected treatment area.

If the subject has a LSR that prevents the investigator or designee from performing the AK count at a visit, the investigator or designee should document in the source document and CRF that the AK count was unable to be obtained due to a LSR.

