8.2.3 PP Population

The per-protocol (PP) population will include all randomized subjects who met all the following requirements:

- met inclusion/exclusion criteria,
- were compliant with the assigned test articles (applied at least 75% and no more than 125% of the expected (120) test article applications, did not miss more than 10 consecutive scheduled applications and have no other evidence of material dosing noncompliance),
- completed the primary endpoint evaluation at Day 90 visit within the designated visit window (± 4 days), and
- had no protocol violations that would affect treatment evaluation.

As exceptions to the above requirements, the following subjects will be included in the PP population as treatment failures if they met the mITT criteria:

- Subjects who are discontinued from the study due to worsening condition that requires alternate or supplemental therapy for the treatment of AK,
- Subjects who are discontinued early from the study due to lack of treatment effect after completing at least four weeks of treatment.

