8.5 Screening and Baseline Assessments

8.5.1 *Demographic and Baseline Characteristics*

Gender, age, race and ethnicity will be summarized by treatment group for the Safety, mITT and PP populations.

Characteristics of the AK lesions in the Treatment Area at Baseline will be summarized including the location, total number of AK lesions and the number of AK lesions at least 4 mm in diameter.

Informed consent information and subject eligibility status will be provided in a listing.

8.5.2 *Medical History*

Medical history at Screening/Baseline will be presented in a subject data listing for the Safety population.

8.5.3 *Prior Medications*

Listings will be provided for the prior medications that were taken and stopped prior to the randomization date.

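### Does the strict >4 mm threshold in the Visit 1 NOTE change who enters the trial or who is analysed?

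*Protocol*

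**What the plan says.** The bullet on lesion counting in Protocol 9.1 contains two statements about size. The first describes what is counted: "which includes any AKs ≥ 4 mm in diameter, as well as any smaller lesions". The second, a NOTE, describes who qualifies: "A minimum of five to a maximum of 10 AKs >4 mm in diameter in the 25 cm² treatment area is required to qualify".

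The entry rule itself is inclusion criterion 4 in Protocol 5.1.1, which requires five to ten "AK lesions, each at least 4 mm in diameter, contained within a continuous 25 cm² treatment area". Protocol 10.1, to which the 9.1 bullet refers the site, restates that baseline requirement inclusively and has staff document "The number and location of AK lesions to be treated that are ≥ 4 mm in diameter". The synopsis, Protocol Sections 1, 4, 9.5 and 9.6, and SAP Sections 4 and 7.1.1 are inclusive too. SAP 8.5.1 summarises "the number of AK lesions at least 4 mm in diameter".

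Two further provisions matter. Exclusion criterion 5 removes anyone who "Has >10 AKs of any size within the treatment area". Protocol 5.1 says what eligibility means: "subjects must meet the following inclusion and none of the exclusion criteria".

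**The concern.** The NOTE is current body text at the step where staff count lesions, and it is worded as a condition of entry. It is the only strict inequality at 4 mm in either document. A subject with four lesions above 4 mm and one of exactly 4 mm has five qualifying lesions under criterion 4 and only four under the NOTE.

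With about 28 sites, some could apply one rule and some the other. Two things might then be at stake. Eligible people could be turned away. And a subject properly enrolled under criterion 4 could later be challenged under the NOTE. Eligibility failures leave the mITT population (Protocol 17.3, SAP 8.2.2), and the PP population requires that subjects "had no protocol violations that would affect treatment evaluation". If such a challenge were decided after unblinding, membership of the primary analysis sets would rest on a discretionary call.

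**Working it through.** **Where the two rules differ.** For each subject let *a* be the number of lesions above 4 mm, *b* the number recorded as exactly 4 mm, and *c* the number smaller.

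- Criterion 4: 5 ≤ a + b ≤ 10.
- NOTE: 5 ≤ a ≤ 10.
- Exclusion 5: a + b + c ≤ 10.

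Exclusion 5 allows C(13,3) = 286 patterns. The rules disagree when a + b ≥ 5 but a ≤ 4. For each total K = a + b from 5 to 10, *a* takes five values (0 to 4) and *c* takes 11 − K values. The number of disagreements is therefore 5 × (6 + 5 + 4 + 3 + 2 + 1) = 105. In all 105, criterion 4 admits and the NOTE rejects.

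The opposite case needs a ≥ 5 with a + b outside 5 to 10. That means a + b > 10, which exclusion 5 forbids, so the count is 0. Hence anyone who passes the NOTE and exclusion 5 also meets the criterion 4 count. The 105 is a count of patterns, not a probability.

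**Can the number of people be estimated?** Two inputs are needed that the documents do not give: the chance *q* that a qualifying lesion is recorded as exactly 4 mm, and the distribution of K. Treating lesions as independent, the rules disagree when more than K − 5 of the K lesions are exactly 4 mm:

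p(K) = 1 − BinomCDF(K − 5; K, q).

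If every site followed the NOTE, the extra screen failures while enrolling 600 would be 600 × p / (1 − p), with p averaged over K. Assumed values give (results from unrounded p):

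| q | Distribution of K | p | Extra screen failures |
|---|---|---|---|
| 1% | 5–10, equally likely | 0.008 | about 5 |
| 5% | 5–10, equally likely | 0.044 | 27.5 |
| 10% | 5–10, equally likely | 0.093 | 61.2 |
| 20% | 5–10, equally likely | 0.208 | 157.5 |
| 5% | 7–10, equally likely | 0.001 | 0.6 |
| 5% | all exactly 5 | 0.226 | 175 |

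At a single q of 5%, the answer runs from under 1 to 175 according to the lesion-count mix alone. These figures show that the size depends on missing inputs; they are not estimates.

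**Does it reach the analysis?**

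1. *Eligibility.* Protocol 5.1 defines it by the listed criteria. Protocol 9.1 has the site confirm those criteria early in Visit 1 and reaffirm them after counting lesions and recording diameters.
2. *Populations.* The mITT and PP definitions (Protocol 17.3, SAP 8.2.2 and 8.2.3) refer to the inclusion and exclusion criteria, not to the visit instructions. A subject enrolled with lesions of exactly 4 mm under criterion 4 meets them.
3. *Arms.* Lesion counting comes before kit assignment, so any extra screen failure precedes randomisation and cannot differ by arm.
4. *Yield.* The targets of at least 558 mITT and 417 PP subjects are drawn from the roughly 600 enrolled. Screen failures are not among them.
5. *Endpoint.* Complete clearance counts all lesions in the treatment area regardless of size (Protocol 17.2.1), so the 4 mm threshold plays no part in scoring Day 90.

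**The case for a change.** The best case for acting is that no sentence says which text prevails, that the NOTE is phrased as a requirement, and that the correction is almost free: one character and a message to sites. If diameters are recorded in whole millimetres, values of exactly 4 mm could be common, and the effect is concentrated at the entry minimum. At an assumed q of 10%, the rules would disagree for 41% of subjects with exactly five qualifying lesions. Settling the point before unblinding would also remove any later argument about population membership.

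Part of this stands. The wording is inconsistent, and some avoidable screen failures are possible. The rest is weaker. Protocol 5.1 is in effect the precedence rule, and the NOTE's own bullet points to Section 10.1, which uses the inclusive threshold. A challenge to an enrolled subject would need someone to treat the NOTE as an eligibility criterion when the population definitions do not, or to argue that a lesion of exactly 4 mm impairs evaluation of an endpoint that counts lesions of every size. Every baseline diameter is recorded, so anyone who falls between the two rules could be identified without new data. It also cannot be fully excluded that the printed symbol is an inclusive sign that lost its lower bar, although the inclusive sign appears intact earlier in the same bullet.

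**Conclusion.** This is a clerical slip and calls for no change to the plan. It works in one direction only: a literal reading of the NOTE could turn away subjects whom criterion 4 admits, and could never admit one whom the criterion 4 count rejects. The number affected is unknown and cannot be derived from the documents.

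Eligibility, both analysis populations, the enrolment yield and the scoring of the endpoint are unchanged, so the equivalence and superiority tests keep their error rates and planned numbers. This conclusion rests on reading eligibility from the listed criteria, as Protocol 5.1 and the population definitions do, and on lesion counting preceding randomisation, as the order of steps in Protocol 9.1 shows. Aligning the symbol would tidy the text without altering any result.

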9.2 Visit 2 (Day 15 \pm 3 days): Phone Call

At this visit, the investigator or designee will:

- Query the subject about any changes in health status or any AEs since the last visit. Document in the AE section of the CRF, as appropriate. NOTE: If severe tolerability issues or a material AE concern of any type are noted, the subject may be scheduled for an in-office visit at the investigator's discretion.
- Record any changes in the subject's concomitant medications and therapies/procedures.
- Review the subject diary and test article compliance.
- Remind the subject to continue to apply test article twice daily, once in the morning and once in the evening, to the skin of the 25 cm² treatment area until the next clinic visit and to bring their tube of test article with them to their next clinic visit.
- Confirm the next appointment and instruct subject to not apply the study medication to the treatment area prior to any study visits.

9.3 Visit 3 (Day 30 \pm 3 days): Follow-Up

At this visit, the investigator or designee will:

- Query the subject about any changes in health status or any AEs since the last visit. Document in the AE section of the CRF, as appropriate.

- Record any changes in the subject's concomitant medications and therapies/procedures.
- Use the transparency and the Baseline photo as necessary to locate the selected treatment area.
- Perform the LSR assessment as described in [Section 10.2](#).
- Review/collect/distribute the subject diary as necessary.
- Review test article compliance. Test article application will be demonstrated if deemed necessary. As necessary, the Baseline photograph and the template may be used as a visual aid to re-instruct subject on proper application of the test article to the treatment area.
- The subject's tube of test article will be weighed and re-dispensed.
- Remind the subject to continue to apply test article twice daily, once in the morning and once in the evening, to the skin of the 25 cm² treatment area until the next clinic visit.
- Confirm the next appointment.

9.4 Visit 4 (Day 45 ± 3 days): Phone Call

At this visit, the investigator or designee will:

- Query the subject about any changes in health status or any AEs since the last visit. Document in the AE section of the CRF, as appropriate. NOTE: If severe tolerability issues or a material AE concern of any type are noted, the subject may be scheduled for an in-office visit at the investigator's discretion.
- Record any changes in the subject's concomitant medications and therapies/procedures.
- Review the subject diary and test article compliance.
- Remind the subject to continue to apply test article twice daily, once in the morning and once in the evening, to the skin of the 25 cm² treatment area until the next clinic visit and to bring their tube of test article with them to their next clinic visit.
- Confirm the next appointment and instruct subject to not apply the study medication to the treatment area prior to any study visits.

9.5 Visit 5 (Day 60 + 4 days): End of Treatment

At this visit, the investigator or designee will:

- Query the subject about any changes in health status or any AEs since the last visit. Document in the AE section of the CRF, as appropriate.
- Record any changes in the subject's concomitant medications and therapies/procedures.
- Use the transparency and the Baseline photo as necessary to locate the selected treatment area.

- Perform the AK lesion count as described in [Section 10.1](#), which includes any AKs ≥ 4 mm in diameter, as well as any smaller lesions.
- Perform the LSR assessment as described in [Section 10.2](#).
- Review and collect the subject diary and test article compliance.
- The subject's tube of test article will be weighed and collected.
- Perform a UPT for all WOCBP.
- Confirm the next appointment.

9.6 Visit 6 (Day 90 \pm 4 days): End of Study

At this visit, the investigator or designee will:

- Query the subject about any changes in health status or any AEs since the last visit. Document in the AE section of the CRF, as appropriate.
- Record any changes in the subject's concomitant medications and therapies/procedures.
- Use the transparency and the Baseline photo as necessary to locate the selected treatment area.
- Perform the AK lesion count as described in [Section 10.1](#), which includes any AKs ≥ 4 mm in diameter, as well as any smaller lesions.
- Perform the LSR assessment as described in [Section 10.2](#).
- Discharge the subject from the study.

9.7 Unscheduled Visit

The investigator may see the subject at an unscheduled visit to manage any AEs or LSRs.

At this visit, the investigator or designee will:

- Query the subject about any changes in health status or any AEs since the last visit. Document in the AE section of the CRF, as appropriate.
- Use the transparency and the Baseline photo as necessary to locate the selected treatment area.
- Perform the LSR assessment as described in [Section 10.2](#).
- Record any changes in the subject's concomitant medications.
- Review subject diary and the requirements for test article application, if applicable.
- Confirm the next appointment.

10. CLINICAL EVALUATIONS

The following clinical evaluations will be performed according to the schedules indicated during the study. The same investigator should complete the evaluations for a given

subject throughout the study. If this becomes impossible a sub-investigator with overlapping experience with the subject and the study should complete the evaluations.

